This trial will assess the impact of e-cigarette warnings on vapers' devices and refills in a randomized clinical trial.

Recruitment: Vapers will first undergo screening online or call the study center to complete the screening survey over the phone. Trial staff will schedule eligible vapers for 2 in-person visits. For each of the 2 visits, vapers will be asked to bring the vapes and refill materials they plan to use over the next 2 weeks.

Informed Consent: Prior to consenting vapers, trial staff will visually inspect photo identification of vapers to confirm that they are 21 years or older. At the beginning of the first appointment, trial staff will explain the consent form and ask the vaper to read the form. Once the participant has finished reading the form, the trial staff member will ask the participant if he or she has any questions. Then both parties will sign the consent form and the participant will receive a copy of the consent form.

Randomization: At the first visit, trial staff will randomly assign participants to one of the three trial arms by using Qualtrics software. Vapers have an equal chance of being randomized to have labels with control, text, or pictorial warnings.

Assessment: Participants will attend 2 in-person appointments at the study office (at Visit 1 and Visit 3 that are spaced 2 weeks apart). The visits will last about 45-60 minutes. At Visit 1 participants will take a survey, have their vape device and refills labeled based on their trial arm, and take another survey. At Visit 3, participants take a survey and have their vape device and refills labeled based on their trial arm. Participants will also be emailed 3 more surveys to complete online at home (taken at Visit 2, 4, and 5). Thus participants will take 5 weekly surveys overall.

Detailed description of the intervention: At each in-person appointment, participants will bring in the vapes and refills they plan to use over the next 2 weeks for labeling. While participants are taking the survey, trial staff will label the devices and refills based on their trial arm.

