Statistical analysis plan

Randomized Clinical Trial Evaluating the Impact of E-cigarette Device Warnings

NCT05714982

2/7/2023, Edited 6/24/2024

Hypotheses

This trial evaluates the impact of e-cigarette health warnings by randomly assigning vapers to have their devices and refills labeled with control messages, text warnings, or pictorial warnings.

The primary hypotheses are about the main trial outcome of vaping quit intentions across the 4 weeks of the trial. We hypothesize that text warnings will elicit higher vaping quit intentions than control messages. We also hypothesize that pictorial warnings will elicit higher vaping quit intentions than text warnings.

For secondary outcomes, we hypothesize that text warnings will elicit higher consumer understanding, information seeking and sharing, and vaping behavior change than control messages, and that pictorial warnings will elicit higher scores on these measures than text warnings. We do not have hypotheses about the impact of the warnings on unintended effects.

Analytic plan

Statistical analyses will use two-tailed tests and a critical alpha of .05.

Primary trial outcome

Vaping quit intentions will be measured using a 3-item scale at 5 time points: post-labeling (Visit 1) and at 1, 2, 3, and 4 weeks (Visits 2-5). The 3 items will be averaged to create a composite quit intention score for each time point. The primary trial outcome will be an average vaping quit intentions score across the 5 time points (i.e., grand mean of quit intentions). We will use all available data in computing 1) the quit intention score at each time point and 2) the aggregate quit intention score across time points. Because the quit intention survey items are forced response, missingness will be uncommon, and the use of two layers of averaging will naturally address most missingness. In the unexpected situation of having no intentions data for a participant, we will set their value to the grand mean for the trial overall (ignoring trial arm).

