We will estimate a general linear model with quit intentions as the continuous outcome and trial arm as a 3-level categorical, between-subjects predictor (pictorial, text, control; text arm will be the reference group). We will not adjust for demographic or other baseline characteristics per CONSORT recommendations (Consort, 2010). We will examine the following variables measured pre-randomization as potential moderators by adding categorical main effects for these terms and their interaction with trial arm: age, education, income, gender, sexual orientation, race, vaping frequency (some days or every day), and current cigarette smoking status. We will probe statistically significant interactions by examining the effect of trial arm within strata of the moderator, using Bonferroni corrections for the post-hoc tests.

We estimated sample size for a 3 arm trial using the following inputs: 80% power, α set at .05, an effect size Cohen's *d* of .16, number of measurements set at 4.2 time points (estimated average number of completed sessions based on our previous cigarette pack labeling trial; Brewer et al., 2016), and an interclass correlation (ICC) of .7 (based on an observed ICC in that trial; Brewer et al., 2016). The previous effect size estimate is based on the average observed *d* in two online experiments (Brewer et al., 2019; Brewer et al., in prep) between pictorial vs text warnings; control vs. text comparisons were larger in these two experiments.

For descriptive purposes, we will examine mean vaping quit intentions at each trial visit, calculating the mean and standard error. We will compare the trial arms graphically at each time point, examining whether means for each trial arm fall outside of the confidence interval for the other arms.

Secondary trial outcomes

Except as noted below, we will again estimate a general linear model for each secondary outcome shown in Table 1, with trial arm as a 3-level categorical, between-subjects predictor (pictorial, text, control; text arm will be the reference group). We will handle missingness as we did for the primary outcome.

Vaping quit attempt and cigarette smoking quit attempts will each be dichotomous outcomes (any quit attempt during the trial). We will estimate a logistic regression model with quit attempt as the outcome and trial arm as the categorial predictor with text arm as the reference group.

Construct	Variable type, range
Consumer understanding	
Knowledge	Continuous, 0-100%

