Cognitive elaboration	Continuous, 1-5
Perceived likelihood of illness from vaping	Continuous, 1-5
Negative affect	Continuous, 1-5
Information seeking and sharing	
Attention to warning	Continuous, 1-5
Information seeking	Continuous, 0-6
Number of conversations in past week	Continuous, 0-100
Vaping behavior change	
Vaping reinforcement attitudes	Continuous, 1-5
Uncontrolled vaping	Continuous, 1-5
Number of times forgoing a vape in past week	Continuous, 0-6 times
Made vaping quit attempt (for 24 hours) in past 4 weeks	Dichotomous, 0 or 1
Successful quitting of vaping (at last survey)	Dichotomous, 0 or 1
Unintended effects	
Inaccurate risk perception	Continuous, 0% to 100%
Stigma	Continuous, 1-5
Smoking quit intentions among dual users	Continuous, 1-5
Made smoking quit attempt (for 24 hours) in past 4 weeks among dual users	Dichotomous, 0 or 1

Table 1. Secondary outcomes

Edit 6/24/2024: In Table 1, changed range of values for information seeking from "Continuous, 1-5" to "Continuous, 0-6". Changed range of values for number of conversations in past week from "Continuous, 1-5" to "Continuous, 0-100". These updates align this document with the main trial registry.

References

Brewer, N. T., Queen, T., Sheldon, J. M., Lazard, A. J., Ribisl, K. M., Ebrahimi Kalan, M., & Hall, M. G. (In preparation). Impact of e-cigarette warnings on perceived message effectiveness.

- Brewer, N. T., Jeong, M., Hall, M. G., Baig, S. A., Mendel, J. R., Lazard, A. J., ... & Ribisl, K. M. (2019). Impact of e-cigarette health warnings on motivation to vape and smoke. *Tobacco Control*, *28*, e64-e70.
- Brewer, N. T., Hall, M. G., Noar, S. M., Parada, H., Stein-Seroussi, A., Bach, L. E., ... & Ribisl, K.
 M. (2016). Effect of pictorial cigarette pack warnings on changes in smoking behavior: A randomized clinical trial. *JAMA Internal Medicine*, *176*, 905-912.

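### The SAP's trial-wide mean fill also applies to the dichotomous secondary outcomes; if the last survey means Visit 5, it shrinks arm differences in successful quitting by the filled share

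*SAP*

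**What the plan says.** The SAP section on secondary trial outcomes states "We will handle missingness as we did for the primary outcome" and makes no exception. The rule it points to, under the primary trial outcome, has two parts. Available items and visits are averaged; if a participant has no data at all, "we will set their value to the grand mean for the trial overall (ignoring trial arm". The SAP defends this on the ground that, with forced-response items, "missingness will be uncommon, and the use of two layers of averaging will naturally address most missingness".

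On models, the SAP says "Except as noted below, we will again estimate a general linear model for each secondary outcome shown in Table 1". The exception that follows is for logistic regression: "Vaping quit attempt and cigarette smoking quit attempts will each be dichotomous outcomes". It changes the model for those two outcomes and gives no other missing-data rule.

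Table 1 lists a third 0/1 outcome, "Successful quitting of vaping (at last survey", which the exception does not name. It therefore falls to the general linear model by default. Neither document says whether the last survey is Visit 5 or the last one each participant completed.

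Two other statements bear on how often a survey is missed. The Protocol, under Assessment, says "Participants will also be emailed 3 more surveys to complete online at home (taken at Visit 2, 4, and 5". The SAP's sample size paragraph uses "number of measurements set at 4.2 time points (estimated average number of completed sessions based on our previous cigarette pack labeling trial".

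**The concern.** The defence of the fill rests on averaging and on forced response. Neither protects a single 0/1 value. There is nothing to average, and a forced-response item cannot prevent an emailed survey from going unopened. The SAP treats a participant without data as an unexpected case for the primary outcome. For successful quitting the same case could be routine, depending on what the last survey means.

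Where the fill is used, each filled participant contributes the same value in every arm, so the arm means are pulled together. What is at stake is the reported size of the effect on quitting, and its interval. Quitting belongs to vaping behaviour change, for which the SAP states directional hypotheses.

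A related problem affects the two quit-attempt outcomes. A fractional fill is not a valid 0/1 value for standard logistic regression.

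**Working it through.** **Inputs from the documents.** About 1,200 participants with equal allocation (Protocol synopsis and Randomization), so about 400 per arm; 5 survey time points; 4.2 completed sessions on average, taken from an earlier trial (SAP sample size paragraph). The plan gives no figure for Visit 5 missingness or for quit rates, so there is none to reproduce.

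**Step 1. Filled share.** Assume that 4.2 means 4.2 of 5 and that Visit 1 is always done. Then 5 − 4.2 = 0.8 surveys are missed per person over Visits 2-5.

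*If the last survey is Visit 5:*
- Missed as often as the Visits 2-5 average: 0.8/4 = 20%.
- Constant dropout: 1 + q + q² + q³ + q⁴ = 4.2 gives q = 0.9127, so 1 − q⁴ = 30.6% lack Visit 5.
- Possible range: 0% (no misses fall there) to 80% (all do).

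*If it is the last completed survey:*
- Item asked only at Visits 2-5: 0.2⁴ = 0.16% have no value if misses are scattered, 1 − q = 8.7% under constant dropout, and at most 0.8/4 = 20%.
- Item also asked at Visit 1: near 0%.

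**Step 2. Effect on the estimate.** Let m be the filled share, p_a the true proportion in arm a, and p̄ the overall observed proportion. The filled arm mean is (1 − m)p_a + m·p̄. With m equal in all arms, p̄ cancels and the difference is (1 − m)(p₁ − p₂).

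Assume quitting of 5/10/15% in control/text/pictorial, so p̄ = 10%:
- 20% filled: pictorial 0.8 × 15 + 0.2 × 10 = 14.0; text 10.0; difference 4.0 points instead of 5.0.
- 30.6% filled: pictorial 0.694 × 15 + 0.306 × 10 = 13.5; text 10.0; difference 3.5 points.

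**Step 3. Effect on the standard error.** The filled values add almost nothing to the residual sum of squares, so the pooled variance is multiplied by about (1 − m), while n is counted as 400 instead of 400(1 − m). The SE ratio, filled to observed cases, is therefore about (1 − m). The average within-arm variance is (0.0475 + 0.0900 + 0.1275)/3 = 0.0883.
- 20%: observed cases √(0.0883 × 2/320) = 2.35 points; filled 0.8 × 2.35 = 1.88.
- 30.6%: observed cases √(0.0883 × 2/277.6) = 2.52; filled 0.694 × 2.52 = 1.75.

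Estimate and SE shrink together, so their ratio, and hence the test, is almost unchanged.

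**Step 4. Simulation.** 400 per arm, missing completely at random with equal shares, three-arm linear model with pooled variance, pictorial against text:

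| Quitting (assumed) | Filled | Estimate | 95% CI coverage, fill | Coverage, observed cases |
|---|---|---|---|---|
| 5/10/15% | 8.7% | 4.6 | 92% | 92% |
| 5/10/15% | 20% | 4.0 | 89% | 92% |
| 5/10/15% | 30.6% | 3.5 | 83% | 92% |
| 8/10/12% | 20% | 1.6 | 93.4% | 93.8% |
| 8/10/12% | 30.6% | 1.4 | 92.3% | 93.9% |

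For the 2-point gap, coverage losses differ slightly between runs: about 0.4 to 0.6 percentage points at 20% and 1.4 to 1.7 at 31%. With 5/10/15%, rejection is 55.9% with the fill and 56.1% on observed cases at 20%, and 50.6% and 50.8% at 31%. With 10% quitting in every arm, rejection is about 5% either way. The 92% for observed cases comes from pooling unequal binomial variances, not from the fill.

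**Step 5. Unequal missingness.** Take 5/10/15% with control 20%, text 15% and pictorial 25% missing:
- p̄ = (0.80 × 5 + 0.85 × 10 + 0.75 × 15)/2.40 = 9.90%.
- Text: 0.85 × 10 + 0.15 × 9.90 = 9.98. Pictorial: 0.75 × 15 + 0.25 × 9.90 = 13.72. Difference 3.7 points.

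With text and pictorial swapped it is 4.2, against 4.0 when shares are equal. So (1 − m) is then only approximate.

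**The case against.** The strongest reply is that the harm hangs on one reading of an undefined term. The SAP's general principle is to use all available data and to keep the fill for people who have none. On that principle the last survey could be the last one completed, and the filled share would be small; below about 10% the effect is minor. That stands, and it makes the point conditional.

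The filled share is also unknown. The 4.2 comes from another trial, and 20% and 31% are scenarios inside a possible 0-80%. The quit rates are assumed too, and the coverage loss depends on the size of the true difference: with a 2-point gap it is small. The proportional shrinkage, however, does not depend on the gap.

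Three stronger readings are tempting, and the documents do not support them.
- *The fill invalidates the tests or costs power beyond that lost to missing data.* With equal missingness, rejection rates match those for observed cases, under the null and the alternative.
- *The interval under-covers because it is falsely precise.* At 20% filled in the 5/10/15% scenario, the estimator's actual spread falls with its SE (2.09 against 2.60 points), and coverage of the shrunken difference is 92%, as for observed cases. The added under-coverage comes from bias toward zero.
- *All 16 secondary outcomes are harmed.* The rule reaches all of them, but for outcomes averaged over visits the fill is used only when a participant has no data, so little should change.

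The linear model for a 0/1 outcome is not an error in itself either; it estimates a risk difference.

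**Conclusion.** The point holds in a conditional form and should be fixed. The SAP applies the trial-wide mean fill to the dichotomous secondary outcomes, and its stated justification does not cover successful quitting.

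If the last survey is Visit 5, the difference in quitting is multiplied by one minus the filled share when missingness is equal across arms, and the interval under-covers the true difference. If it is the last completed survey, the effect is likely to be small. The Visit 5 shares of 20% and 31% assume 4.2 of 5 sessions with Visit 1 always done; the quit rates are illustrations; and the simulations assume missingness unrelated to quitting within arm.

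The damage is to the effect size and interval of one of 16 secondary outcomes. The primary outcome is not affected by this point. For the two quit-attempt outcomes the fill is invalid in form, but only participants with no data would reach it.

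**What to change.** In the SAP section on secondary trial outcomes:

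1. State that the trial-wide mean fill is not used for the three dichotomous outcomes. Analyse observed 0/1 values, or multiply impute from arm, baseline and earlier visits.
2. Define the last survey as Visit 5 or as the last completed survey.
3. Report the number missing by arm for each dichotomous outcome.
4. As a clarification, name the model for successful quitting: logistic regression, as for the quit attempts, or a linear risk difference with unequal-variance standard errors.

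Dropping the fill for the visit-averaged continuous outcomes is optional.

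Counting non-responders as not having quit should be a sensitivity analysis only. In the 5/10/15% scenario it gives the same 4.0 and 3.5 points. With 15% against 25% missing and no true effect, it rejects 8.1% of the time.

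The cost is SAP wording and minor programming, with no new data. Intervals become wider: the observed-case SE is 1/0.80 = 1.25 times the filled SE at 20% missing and 1/0.694 = 1.44 times at 31%. Observed-case analysis still assumes that non-response is unrelated to quitting within arm, which is why the counts by arm matter.

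### Two count outcomes go into a three-arm linear model with a pooled error variance, so the pictorial-vs-text standard error is too small if control is the less variable arm (likely for conversations, either direction for forgoing)

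*SAP*

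**What the plan says.** Under Secondary trial outcomes the SAP states: "Except as noted below, we will again estimate a general linear model for each secondary outcome shown in Table 1". Arm enters as one three-level factor with text as the reference, so pictorial vs text is a coefficient of the model. The one written exception is for the quit-attempt outcomes: "We will estimate a logistic regression model with quit attempt as the outcome".

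Table 1 types both "Number of conversations in past week" (0-100) and "Number of times forgoing a vape in past week" (0-6) as continuous, so both fall under the linear model. The edit of 6/24/2024 widened the conversations range from 1-5 to 0-100, and the model text makes no special provision for it. The SAP mentions no robust or arm-specific variance, count model, transformation or assumption check for either outcome.

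The Hypotheses section expects text to exceed control, and pictorial to exceed text, on information sharing and on vaping behavior change. Pictorial vs text is therefore a hypothesized contrast for both outcomes. The testing standard is: "Statistical analyses will use two-tailed tests and a critical alpha of .05".

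**The concern.** A general linear model, fitted with its defaults, estimates one residual variance from all arms and uses it for every contrast. The SAP does not write this down, but nothing in it departs from the default. For unbounded or nearly unbounded counts, variance usually rises with the mean. If the control arm has fewer conversations, as hypothesized, it probably also has the smaller variance. That smaller variance is averaged into the error term for pictorial vs text, a comparison in which control takes no part.

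The practical risk is a claim that pictures add something over text, made at an error rate above the stated .05. The same pooling makes the text-vs-control test too conservative. Sample size does not cure either error: about 400 per arm makes the arm means close to normal, but the ratio of the model standard error to the true one does not depend on n.

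**Working it through.** **Inputs from the documents.** Two-sided alpha .05 (SAP, Analytic plan); three arms in one model with text as reference (SAP, Secondary trial outcomes); equal allocation (Protocol, Randomization); about 1,200 participants, hence about 400 per arm (Protocol Synopsis). No mean, SD, standard error or power is given for either count outcome, so there is no stated figure for them to reproduce. The sample-size statement concerns the primary outcome and has no bearing here. All variances below are assumptions.

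**Formulas.** Let vC, vT and vP be the control, text and pictorial variances, with n per arm.

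- Model variance of pictorial minus text: (2/n) × (vC + vT + vP)/3.
- True variance: (vT + vP)/n.
- The model value is too small exactly when vC < (vT + vP)/2.
- With vT = vP and r = vC/vT, model SE / true SE = √((2 + r)/3). The actual two-sided alpha is 2 × (1 − Φ(1.96 × that ratio)).
- For text vs control, the SE ratio is √(2(2 + r)/(3(1 + r))).

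**Results, with pictorial truly equal to text.**

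| Warning-arm variance ÷ control | r | Pictorial-vs-text SE ratio | Actual alpha | Text-vs-control SE ratio |
|---|---|---|---|---|
| 1 | 1 | 1.000 | 5.0% | 1.000 |
| 1.25 | 0.8 | 0.966 | 5.8% | 1.018 |
| 1.5 | 0.667 | 0.943 | 6.5% | 1.033 |
| 2 | 0.5 | 0.913 | 7.4% | 1.054 |
| 3 | 0.333 | 0.882 | 8.4% | 1.080 |
| 4 | 0.25 | 0.866 | 9.0% | 1.095 |
| 6 | 0.167 | 0.850 | 9.6% | 1.113 |
| limit | 0 | 0.816 | 11.0% | 1.155 |

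**Conversations.** Take negative binomial counts with variance μ + μ²/k (Poisson as k grows large).

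- Control mean 0.5, both warning arms 1.0: SE ratio 0.913 (Poisson), 0.890 (k = 1), 0.882 (k = 0.5); alpha 7.4% to 8.4%.
- Control mean 0.8, both warning arms 1.0: SE ratio 0.966, 0.952, 0.948; alpha 5.8% to 6.3%.
- Simulation of the first case with k = 0.5 (400 per arm, 20,000 replicates, counts capped at 100): 8.2% rejections with the pooled variance, 4.7% with arm-specific variances.
- Ordered means 0.6, 0.8, 1.0 (control, text, pictorial): SE ratio 0.943 (Poisson), 0.923 (k = 1), 0.916 (k = 0.5). Coverage of the nominal 95% interval is 1 − 2 × (1 − Φ(1.96 × ratio)), or 93.5%, 93.0% and 92.8%. The interval is thus also too short when pictorial does exceed text.

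**Averaging over visits.** The SAP does not say whether these outcomes are averaged over visits like the primary one. With stable person-level differences (k = 0.5), a five-visit mean has variance μ/5 + μ²/k. At means 1.0 and 0.5 this gives 2.2 and 0.6, a ratio of 3.7, against 3/1 = 3 for a single report. Simulated alpha was 8.7% pooled and 4.8% arm-specific. In this case averaging does not remove the problem.

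**Forgoing, 0-6.** Take a binomial shape, variance = mean × (1 − mean/6).

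| Control vs warning-arm mean | Variances | SE ratio | Actual alpha |
|---|---|---|---|
| 1 vs 1.5 | 0.833, 1.125 | 0.956 | 6.1% |
| 2 vs 3 | 1.333, 1.500 | 0.981 | 5.4% |
| 2.5 vs 3.5 | 1.458, 1.458 | 1.000 | 5.0% |
| 3 vs 4 | 1.500, 1.333 | 1.021 | 4.5% |
| 4 vs 4.5 | 1.333, 1.125 | 1.030 | 4.3% |

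Control is lower in every row, yet the standard error may be too small, correct or too large.

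**The case against.** A reader might infer that the pictorial-vs-text standard error is too small whenever control counts are lower. The documents do not support that. The condition concerns the control variance, not the control mean, and the SAP gives neither. The forgoing table shows the reverse near the upper limit. Conversations can reverse too: if 4 of 400 control participants report 60, 100 report 1 and the rest 0, the control mean is 340/400 = 0.85 and the variance 35.5. Against warning arms with mean 1.49 and variance 1.5, the pooled standard error is then far too large.

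The other objections are about size:

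- **The top of the range needs large contrasts.** Simulated rates near 10% come from cases such as control 0.3 vs 1.5 in both warning arms. The SAP's only planning effect is d = .16, for pictorial vs text in sizing the trial on quit intentions, with control vs text described only as larger. With a text-vs-control d of .16 to .25 and k of .3 to 1, rates are about 6.2% to 8.4%. This stands, and is why the modest cases belong in the stated range.
- **The harm is conditional.** If all arms are equal there is no distortion. Inflated false positives need text above control and pictorial equal to text, whereas the SAP expects pictorial above text. This is fair, but a test's error rate is judged under its own null, and the ordered-means case shows undercoverage even if the hypothesis is true.
- **The scope is small.** These are two of 16 secondary outcomes. That stands. It also argues against imposing robust errors on the 1-5 scales or the primary outcome, where no unequal variance has been shown.

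**Conclusion.** The concern holds in conditional form. With a default pooled variance, the pictorial-vs-text standard error is too small if the control variance lies below the average of the two warning-arm variances. That is likely for conversations if the SAP's own hypothesis holds, but not assured; for forgoing the direction cannot be foretold.

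False-positive rates are about 6-7% for modest differences and 7-10% for 2- to 6-fold variance differences, bounded near 11% when the warning-arm variances are equal. The text-vs-control standard error is overstated by about 5-11% over the same 2- to 6-fold range. These figures rest on assumed variances, equal arms, and the default reading of a general linear model. The primary outcome and the sample size are untouched. It is worth correcting because the remedy is cheap and valid in either direction, not because a large error has been shown.

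**What to change.** Keep the linear model and the mean differences. Add one sentence to the SAP under Secondary trial outcomes, stating that heteroscedasticity-consistent (HC3) standard errors will be used for the number of conversations and the number of times forgoing a vape. A negative binomial model for conversations can be listed as an optional sensitivity analysis.

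The cost is one software option, with no new data, visits or participants. The downside is a slightly wider pictorial-vs-text interval when control variance is lower, which is the correction itself. If the variances prove equal, almost nothing is lost at about 400 per arm. If the analysis has already been run, report the HC3 results as a labelled sensitivity analysis.
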